4. STUDY DESIGN

4.1 Overview of Study Design

This study is a multi-center, open label, randomized, phase II trial of the incidence of metabolic syndrome within 12 months in patients treated with enzalutamide in comparison with androgen deprivation therapy for treatment of advanced prostate cancer. This will include patients with biochemically recurrent disease, metastatic disease, and patients offered ADT as primary therapy if they are not candidates for local therapy. Fifty-six patients will be 1:1 randomized to one of two treatment arms with metastasis as a stratification factor. Patients will be treated for a 12-month period continuously and assessed for the development of metabolic syndrome at 3-month intervals.

Treatment will be administered for a 12-month period. Enzalutamide will be taken orally on each day of the cycle. Androgen deprivation therapy will be administered according to standard of care; however, there will be no intermittent dosing of this treatment. Acceptable forms of ADT must result in castrate levels of testosterone (<50ng/dL), and may include: leuprolide, goserelin, histerelin, triptorelin, degarelix, and surgical castration. Toxicity will be evaluated according to National Cancer Institute Common Terminology Criteria for Adverse Events (NCI CTCAE), Version 4.1 ³⁵. Metabolic syndrome will be diagnosed by assessing a patient's blood pressure, waist circumference, fasting glucose, high density lipoprotein (HDL), and triglyceride level and determined according to the Adult Treatment Panel III criteria ³⁶.

Analysis of bone turnover will include measurement of urinary N-telopeptide and serum bone-specific alkaline phosphatase. A dual-energy x-ray absorptiometry scan (DXA) will also be performed at enrollment, month 3 and EOT. This scan will provide information on bone density changes induced by treatment.

Quality of life questionnaires will be administered at each study visit. Physical function changes will be assessed via the Short Physical Performance Battery; the SPPB incorporates 3 validated portions to assess a patient's balance and mobility. Changes in systemic inflammation will be assessed via circulating hs-CRP levels. Additional collection of complete blood counts and chemistries will provide safety information. This testing will occur in the clinic setting every 3 months as well.

Adverse events (AEs) will be assessed; and laboratory values, vital signs, and physical exam will be obtained in order to evaluate the development of metabolic syndrome in patients treated with either enzalutamide or standard androgen deprivation therapy. In addition, we will obtain a PSA every 3 months and radiographic imaging at baseline, 6 months, and 12 months. Patients may remain on study as long as they are deriving clinical benefit, until there is clear progression of disease (per protocol), unacceptable toxicity, or withdrawal of consent.

4.2 Duration of Study

Patients will continue therapy until disease progression, development of unacceptable toxicities, non-compliance, intercurrent illness that prevents treatment continuation, withdrawal of consent, or change in subject condition that render the subject unacceptable for further treatment. If a patient develops

metabolic syndrome, but the patient has at least stable disease and ongoing clinical benefit, then the patient may be allowed to continue on their assigned treatment. The End of Study (9) visit will occur within 30 days after the last dose of study drug, or prior to the start of subsequent anti-cancer therapy. Patients will be assessed for metabolic syndrome over a 12-month period of treatment, as this allows adequate time in which to see the emergence of the metabolic syndrome parameters as well as time for patients to derive a potential clinical benefit from the respective treatment agent. Patients with continued clinical benefit beyond the 12-month endpoint will have the option of remaining on their current therapy with additional follow up visits every 3 months for safety and tolerability assessment. Patients receiving enzalutamide will no longer receive this as a study medication beyond the 12-month time point but may potentially obtain the medication through standard prescribing methods. It is estimated this trial will take 36 months to complete.

4.3 Overview of treatment

During the trial, patients will be assigned to treatment with either enzalutamide or standard of care ADT. For patients randomized to the ADT arm, the choice of type of ADT will be at the discretion of the treating provider. Patients that are in the enzalutamide arm may not also be treated with ADT. In addition, patients on the ADT arm may not also be treated with an androgen-receptor blocker. Anti-androgen therapy may be administered as a single agent \leq 14 days prior to and 14 days following medical castration with a GnRH agonist in order to cover the potential testosterone surge. Intermittent dosing of ADT is not acceptable. Enzalutamide will be dosed at the approved dose of 160mg orally daily. ADT will be administered according to the standard prescribing information for the agent. All subjects should also take at least 1000mg of calcium and 800 International Units (IU) of vitamin D. This treatment will allow protection against bone density loss caused by metastasis or ADT. All subjects will receive this treatment to avoid confounding data, as it is a non-toxic, non-prescription supplement.

4.4 Criteria for Dose Administration

4.4.1 Study Drug Administration

All protocol-specific criteria for administration of study drug must be met and documented prior to drug administration. Enzalutamide or ADT will be administered only to eligible patients under the supervision of the investigator or identified sub-investigator(s).

Patients should be instructed to take their study medication at approximately the same time each day. Enzalutamide can be taken with or without food, patients must swallow capsules whole without chewing, opening or dissolving the capsule. If a patient misses a dose, then they should take it as soon as they remember. If they forget an entire day's dose, they should take their normal dose the next day. They should not take more than their prescribed dose per day.

For any depot-injections of ADT, the site of injection and name of the agent will be recorded. Patients on depot-injections may only be treated with formulations given every 4, 8, or 12 weeks.

4.4.2 Clinical Benefit

Continuation on the trial is dependent on toxicities, as well as evidence of clinical benefit. Patients must not have evidence of radiographic or PSA disease progression as per protocol section 7. Efficacy assessments will be performed via provider assessment. Imaging studies will be obtained every 6 months, or sooner at the discretion of the treating provider. PSA values will be assessed every 3

months, or sooner at the discretion of the treating provider. Patients with progressive disease per section 7 will be ineligible to receive further study treatment.

4.5 Dose Modification Guidelines

Patients will be assessed for toxicities at each study visit, every 3 months. Patients may be evaluated more frequently at the discretion of the treating provider. Toxicities are to be assessed according to the NCI CTCAE, version 4.1. Each AE should be assessed for potential contribution by the study drug. If a patient experiences a grade ≥ 3 toxicity on enzalutamide or an intolerable side effect, withhold dosing for one week or until symptoms improve to grade ≤ 2 . Dosing may resume at the same, or a reduced dose, (per treating physician discretion) for a maximum dose reduction to 80mg daily. Once a dose reduction has occurred, the patient may not re-escalate to a higher dose.

There are no dose modifications for ADT. As stated, this therapy must be dosed continuously and may not be given on an intermittent basis.

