In the randomized clinical trial in patients with metastatic castration-resistant prostate cancer who had previously received docetaxel, 1200 patients were enrolled. The most common adverse drug reactions ($\geq 5\%$) reported in patients receiving enzalutamide in the randomized clinical trial were asthenia/fatigue, back pain, diarrhea, arthralgia, hot flush, peripheral edema, musculoskeletal pain, headache, upper respiratory infection, muscular weakness, dizziness, insomnia, lower respiratory infection, spinal cord compression and cauda equina syndrome, hematuria, paresthesia, anxiety, and hypertension ³³. Severe, grade ≥ 3 adverse events, were reported in 47% patients receiving enzalutamide and 53% of patients receiving placebo. The most common adverse reaction leading to treatment discontinuation in the enzalutamide treated group was seizure, which occurred in 0.9% of the enzalutamide-treated patients compared to none (0%) of the placebo-treated patients. In the Phase III trial, 7 of 800 patients treated with enzalutamide experienced a seizure in comparison to 0 events in the placebo arm. The seizures occurred days 31-603 after drug initiation. No further seizures occurred after patients discontinued enzalutamide. Patients were never readministered enzalutamide while on study, and patients with a history of seizure have been excluded in additional studies. It is thought that the mechanism of seizure may be the inhibition of the GABA-gated chloride channel. It is suggested that enzalutamide may lower the seizure threshold but not directly contribute to these events. This trial will exclude patients with a predisposition to seizure, as the exclusion of this subset of patients should not have a known impact on altering the incidence of metabolic syndrome. Another notable adverse event associated with the enzalutamide treatment arm is fall and fall-related injuries. This occurred in 4.6% of patients enrolled in the randomized trial and assigned to the enzalutamide treatment group in comparison to 1.3% of patients treated with placebo. The mechanism of fall is not clear. Fall-related injuries are described as joint injuries, non-pathologic fractures, and hematomas.

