14. Clinically significant cardiovascular disease as evidenced by: Myocardial infarction within 6 months of screening; uncontrolled angina within 3 months of screening; New York Heart Association (NYHA) class 3 or 4 congestive heart failure; clinically significant ventricular arrhythmia; Mobitz II/2nd degree/or 3rd degree heart block without a pacemaker in place; uncontrolled HTN (systolic >180 mmHg or diastolic >105 mmHg at screening)
15. Previous exposure to enzalutamide
16. Use of an investigational therapeutic within 30 days
17. History of gastrointestinal disorders (medical disorders or extensive surgery) that may interfere with the absorption of the study agent
18. Known or suspected brain metastasis or active leptomeningeal disease
19. History of seizure or any condition that may predispose to seizure (e.g., prior cortical stroke, significant brain trauma) at any time in the past. Also, history of loss of consciousness or transient ischemic attack within 12 months of Day 1 visit
20. Have any condition that, in the opinion of the investigator, would compromise the well-being of the subject or the study or prevent the subject from meeting or performing study requirements

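### The enzalutamide hold-and-resume rule in section 4.5 makes no exception for seizure, and no other section requires stopping after one

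*Combined protocol and SAP*

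**What the plan says.** **Dose rule (4.5).** For a grade 3 or higher "toxicity on enzalutamide or an intolerable side effect, withhold dosing for one week or until symptoms improve to grade" 2 or lower. Then "Dosing may resume at the same, or a reduced dose, (per treating physician discretion) for a maximum dose reduction to 80mg daily". No type of event is excepted.

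**Background (1.5).** In the cited randomized trial, 7 of 800 men on enzalutamide had a seizure, against none on placebo. "The most common adverse reaction leading to treatment discontinuation in the enzalutamide treated group was seizure", at 0.9%. The section adds: "No further seizures occurred after patients discontinued enzalutamide". And: "Patients were never readministered enzalutamide while on study, and patients with a history of seizure have been excluded in additional studies". On mechanism it is guarded: "It is suggested that enzalutamide may lower the seizure threshold but not directly contribute to these events".

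**Entry (5.2, item 19).** The exclusion reads "History of seizure or any condition that may predispose to seizure", at any time in the past.

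**Stopping.** Section 4.1 keeps patients on study "until there is clear progression of disease (per protocol), unacceptable toxicity, or withdrawal of consent". Section 4.2 has a similar list and adds a change in the patient's condition that makes further treatment unacceptable. Section 4.4.2 makes continuation depend on toxicities. Section 7.8 refers to unacceptable toxicity in its completion paragraph, and lists adverse event among the reasons for which a patient may be withdrawn. None of these defines unacceptable or names seizure.

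**Oversight.** Section 7.6 has the principal investigator oversee each subject's care and safety. Section 11.1 provides for working-group discussion of each subject, with toxicities and dose modifications minuted, and for monthly calls between sites. Serious events go to the DSMC, within 5 business days under 11.1 and within 48 hours under 12.1.

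**The concern.** Seizure is the one toxicity that the protocol singles out for exclusion at entry. Once treatment starts, it falls under the same rule as any other toxicity. Section 4.5 then raises two problems.

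- A seizure is a discrete event whose symptoms may clear quickly. The improvement condition could be met soon after the event, and full-dose resumption at 160 mg would then be within the rule.
- A seizure below grade 3 that nobody calls intolerable does not reach the threshold for a hold.

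What is at stake is patient safety and, secondarily, uniform handling. After an on-study seizure, the decision to re-dose rests with the treating physician under general oversight. The man would by then have a history that would have kept him out of the trial.

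**Working it through.** **Step 1. Does any rule require a stop?** Seizure is mentioned only in 1.5 and in exclusion 19. The candidate rules compare as follows.

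| Section | What it does | Requires stopping after a seizure? |
|---|---|---|
| 4.1, 4.2, 7.8 (completion) | Ends treatment for unacceptable toxicity | Only if judged unacceptable; term undefined |
| 4.4.1 | Drug given only to eligible patients | Carrying exclusion 19 into treatment is possible but not stated |
| 4.4.2 | Continuation depends on toxicities | No event named |
| 7.8 (withdrawal list) | Patient may be withdrawn for an adverse event | Permissive |
| 7.6, 11.1 | Investigator oversight and minuted review | No step decides re-dosing |
| 11.1, 12.1 | Reporting to the DSMC, which can suspend or close the trial | No step decides one man's re-dosing |

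The protocol does write mandatory, event-specific rules elsewhere. PSA progression requires discontinuation (7.2.1), radiographic progression requires removal (7.2.2), and an unavoidable strong CYP2C8 inhibitor requires reduction to 80 mg (7.7). A named rule for seizure would be in keeping with that style.

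**Step 2. Reproduce the cited rate.** 7/800 = 0.00875, or 0.875%, which rounds to the stated 0.9%. The exact (Clopper-Pearson) 95% interval takes the 2.5% point of Beta(7, 794) and the 97.5% point of Beta(8, 793), giving 0.003525 to 0.017945.

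**Step 3. Apply it to this trial.** Section 10.1 plans n = 28 men on enzalutamide. With a binomial count and p = 0.00875:

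- Expected seizures: 28 × 0.00875 = 0.245.
- P(none) = 0.99125^28 = 0.782.
- P(exactly one) = 28 × 0.00875 × 0.99125^27 = 0.193.
- P(at least one) = 1 − 0.782 = 0.218.
- P(two or more) = 0.0249.

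| Quantity | At 7/800 | Over the 95% interval |
|---|---|---|
| Expected seizures | 0.245 | 0.099 to 0.502 |
| None | 78.2% | 60.2% to 90.6% |
| Exactly one | 19.3% | 9.0% to 30.8% |
| At least one | 21.8% | 9.4% to 39.8% |
| Two or more | 2.5% | 0.4% to 9.0% |

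**Step 4. Allow for a lower risk.** The cited trial enrolled men with castration-resistant disease, and its seizures occurred as late as day 603. Here predisposed men are excluded and treatment lasts 12 months. The documents do not say how much lower the risk would be, so two assumptions are shown:

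- Half the rate: 1 − (1 − 0.004375)^28 = 11.6%.
- A quarter of the rate: 1 − (1 − 0.0021875)^28 = 5.9%.

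**Step 5. What the figure measures.** Re-dosing after a seizure needs both a seizure and a decision to resume:

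P(seizure and re-dosing) = P(seizure) × P(re-dosing given seizure) ≤ P(seizure).

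The documents give nothing from which to estimate the second factor, so at the cited rate 21.8% is a ceiling. Different handling of two men needs at least two seizures, so its ceiling is 2.5%. The counts cover seizures of any grade, because the documents give no split by grade.

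**The case against.** The strongest reply is that 4.5 is a guideline for men still fit to continue, read alongside the general stops and the oversight in 7.6 and 11.1. An investigator can stop a man after a seizure, and more than one person reviews the case. This stands. A reader might infer that the protocol directs re-dosing, or that nothing restrains it. The documents support neither: resumption is permitted, not ordered, and real discretionary stops exist. The remaining gap is that none is mandatory for seizure.

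Second, entry criteria are not continuation criteria here. Metabolic syndrome is exclusion 4, yet men who develop it may stay on treatment. Testosterone below 50 ng/dL is exclusion 5, yet the ADT arm must reach it. That is correct, so exclusion 19 does not by itself imply a stopping rule. But those two are a study outcome and an intended drug effect, whereas exclusion 19 is a safety precaution.

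Third, 1.5 describes what an earlier trial did and says the drug may lower the threshold without directly contributing. A reader might infer that rechallenge has been shown to be dangerous. It has not: no man was rechallenged, so the text shows neither harm nor safety. The argument rests on precedent and caution.

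Fourth, a mandatory stop ignores attribution, although 4.5 asks for each adverse event to be assessed for drug contribution. A man whose seizure has a clear other cause would lose his study drug. That is a real cost, but exclusion 19 already bars a seizure history whatever its cause.

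Finally, the investigator's brochure and the cited prescribing information were not available, so whether they address seizure could not be checked. Section 4.5 does not refer to them.

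**Conclusion.** The point holds as a gap in a stated safety rule. Followed as written, 4.5 permits full-dose resumption after a seizure, and no other section requires a stop. This falls short of the precedent reported in 1.5 and of the caution in exclusion 19. The general safeguards narrow the gap but do not close it.

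The size is modest. Transferring the 7/800 rate to 28 men, with independent events, gives about a one-in-five chance that the rule is tested at all, and probably less in this population. It would be wrong to read that as the chance of a man being re-dosed or harmed, for which the documents give no basis. The change is still worth making because the event is serious and foreseeable and the amendment is small. Confidence is medium, since the case rests on the protocol's own caution and not on rechallenge data.

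**What to change.** Add to 4.5: *A seizure of any grade is outside the hold-and-resume rule and requires permanent discontinuation of enzalutamide.* In 7.8, list seizure on enzalutamide as a mandatory reason to stop study drug, separate from the permissive withdrawal list.

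The cost is one sentence and one line, by amendment. Any man with an on-study seizure, including one with a clear alternative cause, loses the option of rechallenge and stops enzalutamide early. At the cited rate that is about 0.25 men, and most likely none. Sample size and analysis are unaffected.

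The same amendment could settle whether serious events reach the DSMC within 48 hours or within 5 business days.

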4.6 Study specific biomarker collection

Plasma samples will be obtained and stored for future correlative analysis regarding potential identified biomarkers important in the development of metabolic syndrome or prostate cancer progression. Approximately 3 7mL tubes of blood will be drawn. De-identified tubes will be processed and stored for future analysis. See lab manual for processing instructions.

5. STUDY POPULATION

5.1 Inclusion Criteria

Each patient must meet all of the following inclusion criteria to be enrolled in the study:

1. Histologically or cytologically proven adenocarcinoma of the prostate. If pathology is unavailable, the PI may also make a determination of prostate cancer based on unequivocal clinic data.
2. Patients with advanced prostate cancer suitable for systemic treatment defined as: having metastatic disease, a biochemical relapse after primary therapy, or patients in whom primary therapy is not appropriate or feasible. Patients without metastatic disease will need evaluation for local therapy and deemed inappropriate or have refused this treatment option
3. ECOG 0-2
4. Age > 18 years old
5. Must use a condom if having sex with a pregnant woman
6. A male patient and his female partner who is of childbearing potential must use 2 acceptable methods of birth control (one of which must include a condom as a barrier method of contraception) starting at screening and continuing throughout the study period and for 3 months after final study drug administration
7. Life expectancy estimated at > 12 months
8. Ability to understand and willingness to provide written informed consent document

5.2 Exclusion Criteria

The following are criteria for exclusion from participating in the study:

1. A history of androgen deprivation therapy.

- a. Patients receiving hormonal therapy in the adjuvant and/or neoadjuvant setting must have discontinued therapy at least 6 months prior to day 1 of treatment
- b. AND have a serum testosterone level ≥ 50 ng/dL
- c. AND cannot have received more than 18 months of previous ADT.
2. A history of orchiectomy
3. Previous androgen blockade (e.g. antiandrogens) given for greater than 2 weeks in the last 3 months. Anti-androgens used during the initiation of ADT to avoid a flare phenomenon are acceptable for up to 4 weeks.
4. Patients already meeting the criteria for metabolic syndrome as defined by the Adult Treatment Panel III Criteria which requires 3/5 parameters below. *Patients with 2 of the parameters at baseline will be allowed enrollment provided that one of those risk factors is hypertension ($\geq 130/\geq 85$ mm Hg).*
 - a. Abdominal obesity, defined as a waist circumference >102 cm (>40 in)
 - b. Serum triglycerides ≥ 150 mg/dL (1.7 mmol/L) or drug treatment for elevated triglycerides
 - c. Serum HDL cholesterol <40 mg/dL (1 mmol/L) or drug treatment for low HDL
 - d. Blood pressure $\geq 130/\geq 85$ mmHg or drug treatment for elevated blood pressure
 - e. Fasting plasma glucose (FPG) ≥ 100 mg/dL (5.6 mmol/L) or drug treatment for elevated blood glucose
5. Baseline hypogonadism as defined as a testosterone <50 ng/dL
6. PSA <0.5 ng/dL
7. Serum Vitamin D 25, OH <12 ng/mL
8. Active Hepatitis C virus
9. Use of corticosteroids as defined by a daily dose of prednisone (or equivalent) of 5mg or greater for more than 1 month continuously within 3 months of screening
10. Corrected calcium >10.6 mg/dL
11. Absolute neutrophil count $<1500/\mu\text{L}$; platelet count $<100,000/\mu\text{L}$, hemoglobin <9 g/dL
12. Total bilirubin $\geq 1.5 \times \text{ULN}$ (unless documented Gilbert's); alanine aminotransferase or aspartate aminotransferase $\geq 2.5 \times \text{ULN}$
13. Creatinine >2 mg/dL
14. Clinically significant cardiovascular disease as evidenced by: Myocardial infarction within 6 months of screening; uncontrolled angina within 3 months of screening; New York Heart Association (NYHA) class 3 or 4 congestive heart failure; clinically significant ventricular arrhythmia; Mobitz II/2nd degree/or 3rd degree heart block without a pacemaker in place; uncontrolled HTN (systolic >180 mmHg or diastolic >105 mmHg at screening)
15. Previous exposure to enzalutamide
16. Use of an investigational therapeutic within 30 days
17. History of gastrointestinal disorders (medical disorders or extensive surgery) that may interfere with the absorption of the study agent
18. Known or suspected brain metastasis or active leptomeningeal disease
19. History of seizure or any condition that may predispose to seizure (e.g., prior cortical stroke, significant brain trauma) at any time in the past. Also, history of loss of consciousness or transient ischemic attack within 12 months of Day 1 visit
20. Have any condition that, in the opinion of the investigator, would compromise the well-being of the subject or the study or prevent the subject from meeting or performing study requirements

